### 8.3.6 Pregnancy Tests

A serum or urine  $\beta$ -HCG pregnancy test will be performed for all female patients of childbearing potential at baseline, within 28 days prior to first study treatment.

Post-menopausal status (for female patients <60 years of age) must be proven by one of the following:

- History of hysterectomy
- Last spontaneous bleeding at least 1 year prior to informed consent and negative  $\beta$ -HCG
- Serum estradiol <20 pg/mL and FSH >40 IU/L

During the course of the study, pregnancy tests will be repeated monthly until end of study in female patients of childbearing potential. At the first dosing visit (D0), a pregnancy test does not need to be

performed if the baseline pregnancy test result is not older than 14 days. Since after month 12 and during the 2nd year (months 12-27), visits are performed in three monthly intervals, female patients of childbearing potential will be provided with pregnancy test strips for the performance of pregnancy tests at home during months: 13, 14, 16, 17, 19, 20, 22, 23, 25, and 26. The study sites/Investigators will collect and register information on the outcome of the tests via telephone contacts.

A female patient who becomes pregnant during the treatment phase of the study must be discontinued from study treatment. SAE reporting/pregnancy reporting and pregnancy monitoring and follow-up will be performed as described in Sections 8.3.1.1 – pregnancy – and 8.3.2.5.

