## **4.6 End of the Study**

For regulatory purposes, the end of the study is defined as the last visit of the last patient or the last date of follow-up of toxicities, if required (whichever is later).

The end of study for each individual patient is the visit at month 30, unless disease progression, withdrawal from the study, or death occurs earlier.

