### 7.3 Treatment Phase

Adverse events and concomitant medication are to be reported continuously from Day 0 until end of study. AEs ongoing at EOS have to be followed up until resolved or for a period up to a maximum of 30 days by the investigator (see Section 8.3.2.3). Pregnancy tests are to be performed monthly in all female patients from the start of treatment until EOS.

#### 7.3.1 Month 0

##### 7.3.1.1 Day 0

The following examinations and procedures will be performed on day 0:

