**7.3.9 Second Year**

During the second year of the study, patients in the everolimus arm continue on everolimus, while patients in the  $^{177}\text{Lu}$ -edotreotide arm will not receive further PRRT treatment until diagnosis of progression. Study visits during the 2nd year take place on an out-patient basis in 3-monthly intervals (12, 15, 18, 21, 24, and 27 months after day 0, with  $\pm 21$  day time window). For the management of patients impacted by the follow-up extension, see Section 3.1. Examinations comprise physical examination, vital signs, blood sampling for laboratory and tumour markers, pregnancy test, EORTC QLQ questionnaire, recording of AEs and concomitant medication, morphological MRI/CT imaging at every second year visit, as well as 12-lead ECG and  $^{99\text{m}}\text{Tc}$ -MAG3 renal scintigraphy at months 12, 18, and 24 only. Morphological MRI/CT imaging and  $^{99\text{m}}\text{Tc}$ -MAG3 renal scintigraphy should be performed within 7 days prior to the study visit, in order for the results to be available at the time of the visit. Pregnancy tests for the following months without visits at the study centre will be handed out to the patients at every visit. Blood-sampling can be performed up to 72 hours prior to each visit according to local practice and as clinically appropriate. Pregnancy tests are to be repeated monthly during year 2 until EOS. Everolimus patients continue to receive their patient diary at every visit.

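### The home pregnancy-test list in Protocol 8.3.6 stops at month 26 and omits months 28 and 29, contrary to the protocol's own monthly-until-EOS rule

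*Protocol*

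**What the plan says.** Protocol 8.3.6 states the general rule first: "pregnancy tests will be repeated monthly until end of study in female patients of childbearing potential". It then explains why home tests are needed: "Since after month 12 and during the 2 nd year (months 12-27), visits are performed in three monthly intervals". On that basis it provides strips for "pregnancy tests at home during months: 13, 14, 16, 17, 19, 20, 22, 23, 25, and 26", and it asks sites to obtain and record the results by telephone.

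Other sections bear on the same period:

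- 4.6 fixes the individual end of study: "The end of study for each individual patient is the visit at month 30, unless disease progression, withdrawal from the study, or death occurs earlier".
- 7.3.9 places the later visits at "12, 15, 18, 21, 24, and 27 months after day 0, with $\pm 21$ day time window". The EOS visit at month 30 follows (7.3.10).
- 7.3.9 repeats the frequency: "Pregnancy tests are to be repeated monthly during year 2 until EOS". It also has a supply rule that names no months: "Pregnancy tests for the following months without visits at the study centre will be handed out to the patients at every visit".
- 7.3 says: "Pregnancy tests are to be performed monthly in all female patients from the start of treatment until EOS".
- Footnote D to both flow charts (Tables 1 and 2) also requires monthly repetition until EOS.
- The synopsis has everolimus taken daily until progression or EOS.

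**The concern.** Section 8.3.6 is the dedicated pregnancy-test section. It is the only place that names the home-test months and the only place that states how home results reach the site. A coordinator preparing a worksheet or ordering strips would naturally start there. Its list ends at month 26, yet participation runs to month 30, and an everolimus patient without progression is still on drug in months 28 and 29. The protocol itself cites known embryotoxicity and fetal toxicity of the reference drug (8.3.1.1) and requires study treatment to stop if a patient becomes pregnant (4.4.1, 8.3.6). A site that follows the list would omit two tests and would deviate from the monthly rule in the same paragraph.

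**Working it through.** The plan gives no figure to reproduce, so the check is a count.

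**Inputs.** Site visits are monthly from month 0 to month 11, then at months 12, 15, 18, 21, 24 and 27 (7.3.9), with EOS at month 30 (4.6, 7.3.10). Listed home-test months are 13, 14, 16, 17, 19, 20, 22, 23, 25 and 26, which is 10 months (8.3.6).

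**Step 1: months that need a home test under monthly testing to EOS.** Removing the visit months from 12 to 30 leaves 13, 14, 16, 17, 19, 20, 22, 23, 25, 26, 28 and 29, which is 12 months.

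**Step 2: months with neither a visit nor a listed home test.** Across months 0 to 30 these are exactly 28 and 29 (12 − 10 = 2).

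**Step 3: which schedule the list fits.**

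| Schedule ends at month | Non-visit months after month 12 | Same as the 10 listed? |
|---|---|---|
| 24 | 8 | No |
| 27 | 10 | Yes, month for month |
| 30 | 12 | No |

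The list is complete for its own stated window of months 12 to 27, and that window stops one visit interval before EOS. This suggests that the list was not carried through to month 30 when follow-up was lengthened from 24 to 30 months. That is an inference; no text says so.

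**Step 4: what the other sections imply for months 28 and 29.** The 7.3.9 supply rule applies at every visit. Month 27 is one of the visits named there, and the months without a visit that follow it are 28 and 29. Read together with the monthly rule, 7.3.9 therefore covers both the requirement and the supply. It says nothing about collecting results; that duty stands only in 8.3.6, directly after the list.

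**Step 5: interval if a site uses only the 8.3.6 list.** Month 27 to month 30 is 3 × 30 = 90 days nominally, against about 30 days under the monthly rule. Both visits carry a ±21-day window, so the extreme is 90 + 21 + 21 = 132 days.

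**Step 6: who is on drug in that interval.** Assume exponential PFS with the planning median of 11.0 months for everolimus (Protocol 9.4). The fraction progression-free at month 27 is 0.5^(27/11) = 0.5^2.45 ≈ 0.18, or about 18 of the 100 planned everolimus patients. That is before dropout and before restricting to women of childbearing potential, a fraction that the documents do not give. In the <sup>177</sup>Lu-edotreotide arm the last scheduled dose is at day 270, and 270 + 66 = 336 days, so the 66-day post-treatment contraception period is over by about month 11.

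**The case against.** The strongest answer is that nothing is missing from the protocol read as a whole. Monthly testing to EOS is stated in 7.3, in 7.3.9, in footnote D of both flow charts and in 8.3.6 itself. The 7.3.9 supply rule puts tests for months 28 and 29 in the patient's hands at month 27. The list in 8.3.6 is introduced for months 12 to 27, so it does not claim to exempt the later months. The telephone sentence refers to test outcomes generally and is not expressly limited to the listed months. Contraception or abstinence is required throughout the study in both arms, so the test is a second check.

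Most of this stands. It rules out the stronger reading that a reader might take from the list alone, namely that months 28 and 29 have no test, or that a 90-day interval is built into the plan. The documents do not support that: the long interval arises only if a site works from the list and overlooks both the monthly rule and the supply rule.

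Two things remain. The only month-by-month list disagrees with the rule that it is meant to carry out. And the only statement on collecting home results follows directly after that list, so whether it extends to months 28 and 29 is left for the site to infer.

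**Conclusion.** The point holds as an internal contradiction of low severity. The 8.3.6 list and its months 12 to 27 wording omit 2 of the 12 non-visit months between month 12 and EOS, against the monthly-until-EOS statements in four places (8.3.6 itself, 7.3, 7.3.9 and the flow-chart footnotes) and the hand-out rule in 7.3.9. The count rests only on the visit schedule and on month 30 as EOS, and is certain.

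The consequence is conditional. For a site using only the list, about 90 days would separate the month-27 and month-30 tests. The patients mainly concerned are women of childbearing potential on everolimus who are progression-free past month 27. Under the exponential assumption they are some part of roughly 18% of that arm, and the documents do not allow a closer figure. No endpoint, analysis or other statistical quantity is affected.

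**What to change.** Reconcile the stated window and the month list in 8.3.6 with 4.6, 7.3, 7.3.9 and footnote D of Tables 1 and 2, so that all of them say the same about months 28 and 29. The reconciled text should cover both the supply of strips and the telephone collection of results, since the latter appears only in 8.3.6. No new clinical rule is needed; the sections only have to agree.

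The cost is about one line of protocol text. If the sections are aligned on the monthly statement, it also means two test strips and two results to collect for each affected patient.

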### 8.3.7 12-Lead ECG

A 12-Lead ECG will be recorded after 5 minutes supine rest at the following points of time:

- At baseline, within 28 days prior to first study treatment
- Study visits of treatment phase (months 0 - 11): at 0, 3, 6, 9 months
- Study visits of 2nd year (months 12 - 24): at 12, 18, and 24 months
- At EOS visit

Subjects randomised into the Lu-edotreotide group will have additional ECGs at 72 h after each dose administration.

Rhythm, RR-, HR-, PR-, QT-, QTc- and QRS-intervals will be assessed at each point of time that a 12-lead ECG is recorded. The ECG printout will be included in the patient's file, and the investigator will comment on whether the results are normal, abnormal (not clinically significant) or abnormal (clinically significant).

### 8.3.8 Renal Scintigraphy (99mTc-MAG3)

Within 28 days prior to randomisation, each subject will undergo 99mTc-MAG3 (99mTc-mercaptoacetyltri-glycine) renal scintigraphy, to assess the baseline tubular extraction rate (TER) of the kidneys and evaluate the kidney functionality from renogram and sequence images. Follow-up 99mTc-MAG3 renal scintigraphy will be performed in 6-monthly intervals in both groups: at month 6, 12, 18, 24, and 30. For the Lu-edotreotide arm, the month 6 99mTc-MAG3 renal scintigraphy has to be performed within 7 days before administration of the cycle D3 dose of study drug. In case an additional 99mTc-MAG3 renal scintigraphy is prescribed to allow dosing up to 29 Gy to the kidney, it also has to be performed before dosing of study drug (see Section 3.1).

The renal scintigraphy will be performed as clinically established, but in accordance with the details defined in the Clinical Imaging Manual (CIM).

### 8.3.9 Kidney Function and GFR

Kidney function will be monitored assessing

- Quantitative TER (see Section 8.3.8) determined at baseline, and thereafter in 6-monthly intervals

- GFR calculated from serum creatinine, determined at baseline, thereafter in 3-monthly intervals.
- The calculated GFR will be determined centrally for consistency. Body weight, and height, as well as sex and age will be recorded in the CRF.
- Kidney volume (abdominal MRI/CT, baseline, 3-monthly interval).
- GFR will be calculated using the recommended CKD-EPI formula (Levey et al., 2009)

## 8.4 Pharmacogenomics

Not applicable.

## 8.5 Total Volume of Blood

Blood volumes drawn for safety evaluations correspond to those used in clinical routine for patients with GEP-NET. In addition, blood for tumour marker analyses will be drawn.

Total volume of samples will not exceed 50 mL / month. They are summarised in [Table 7](#).

Patients in Sub-study C will also have a total of 11 mL of blood taken for dosimetry within 7 days.

**Table 7: Total Volume of Blood**

Sample	Volume per Sample [mL]	Number of Samples	Total Volume [mL]
Haematology			
Screening	3	1	3
Months 0-11	3	20 x 1	60
2 nd year, EOS	3	7 x 1	21
Biochemistry A			
Screening	7.5	1	7.5
Months 0-11	7.5	20 x 1	150
2 nd year, EOS	7.5	7 x 1	52.5
Clotting parameters			
Screening	3	1	3
Months 0-11	3	12 x 1	36
2 nd year, EOS	3	7 x 1	21
TER by 99m Tc-MAG3 renal scintigraphy			
Screening	7.5	1	7.5
Month 6 ( optional M 9 )	7.5	1 (x1)	7.5 (7.5)
Months 12, 18, 24	7.5	1 x 3	22.5
EOS	7.5	1	7.5
Overall TOTAL		83	399.0 (406.5)
A including tumour markers; including pregnancy test (if not performed from urine)			

### 8.6.2 Electronic File Transfer

Where possible, all image data are transferred using ABX-DIRECT® software as described in the Clinical Imaging Manual. If ABX-DIRECT® is not available, image data will be transferred via DVD by pick up postal service.

### 8.6.3 Other Samples

Samples for analysis of chromogranin A (and other tumour marker samples, if applicable; see Section 8.2.1.3), pregnancy status and clinical laboratory will be analysed in the institutional laboratories of each site according to local specifications.

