### 4.3 Recruitment

Potential patients for this study will be recruited by approximately 60 oncological centres in Europe, North America, South Africa and Australia specialised in endocrine oncology (endocrinology, gastroenterology, nuclear medicine), and with local access to or own experience in PRRT. Study sites will be interdisciplinary, consisting of an endocrine oncology sub-site, and a nuclear medicine sub-site. Study visits will be typically conducted at the recruiting sub-site, or as institutionally appropriate. Treatment visits for patients randomised to  $^{177}\text{Lu}$ -edotreotide will be performed in the collaborating nuclear medicine sub-site. Patients will be invited for study participation by the investigators in the context of specialised NET clinics. Interested patients will be provided with an information sheet and will undergo a detailed informed consent procedure prior to any study procedures (see Section 13.2). Recruitment will be continued until a sufficient number of patients has received at least one dose of PRRT treatment, or a sufficient number of events has been reached.

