## **7 Schedule of Evaluations and Visit Description**

### **7.1 Schedule of Evaluations**

A detailed schedule of evaluations is shown in [Table 1](#) and [Table 2](#).

If more than one procedure is scheduled at the same time, the assessments will be performed in an order as clinically appropriate.

As an exception only during the COVID-19 pandemic, if a patient is unable to attend his/her institutional site visit per the protocol schedule, blood samples may be collected and tested in the patient's local centre in a laboratory certified as per local requirements. However, the physical examination, vital signs, and electrocardiogram (ECG) may be postponed to the next scheduled site visit. Any of these deviations from the protocol-specified schedule will be considered a minor protocol deviation. The principal investigator (or delegate) will follow up on the patient's status as needed.

Protocol measures introduced because of the COVID-19 outbreak are temporary (see also [Section 5.6.2](#)), and will be considered revoked as soon as there is a consensus that the period of the current public health crisis has passed.

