### 8.3.5 Clinical Laboratory Tests

Blood and urine samples for clinical laboratory parameters will be collected for all subjects at the points of time given in [Table 1](#) and [Table 2](#).

Laboratory assessments will be performed by the institutional or local laboratories. Because of the potential for radioactivity in some blood and urine samples, the local laboratory must adhere to their SOPs and/or any guidance and regulations for handling radioactive substances.

Lu-edotreotide arm ONLY: at study site wherever possible. If not logistically feasible, inter-visit lab samples can be taken by a medical general practitioner (GP) in the vicinity of the patient's home.

Samples will be tested for the following parameters:

Haematology: haemoglobin, haematocrit, mean corpuscular volume (MCV), mean corpuscular haemoglobin (MCH), white blood cell count (total and differential: leukocytes, neutrophils, eosinophils, basophils, lymphocytes, monocytes), red blood cells, platelets.

Biochemistry: sodium, potassium, chloride, calcium, glucose, creatinine, urea, albumin, total bilirubin, aspartate transaminase (AST), alanine transaminase (ALT), alkaline phosphatase (AP), gamma-glutamyl transferase (GGT), lipase, amylase, total protein.

Clotting parameters: prothrombin time (quick), reagent-independent prothrombin ratio (international normalised ratio; INR), activated partial thromboplastin time (aPTT).

Urinalysis (dipstick accepted): specific gravity, pH, protein, glucose, blood, leukocytes, ketones, nitrite, albumin, creatinine. Alpha-1-microglobulin will also be tested in urine but only in centres with adequate technical equipment and an established test method.

Tumour marker: Chromogranin-A, further markers (see Section [8.2.1.3](#)).

The investigator will sign each laboratory printout and assess clinical significance. Clinically significant values have to be highlighted as "c.s." (clinically significant). The printouts will be included in the patient's file.

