5.8 Multi-centre Studies

Individual centre results will not be summarised. In doubt of underlying centre effects, they may be explored where deemed appropriate or necessary.

6 Summary of Study Data

Progression-free survival (PFS), overall survival (OS), and other time-to-event data will be analysed using the Kaplan-Meier method, the Cox's proportional Hazard model (for hazard ratio computation) and the Log-rank test (stratified for the main analysis, non-stratified on randomization factors where needed for sensitivity analysis).

For OS, the main analysis will take into consideration new anti-cancer treatment starts and/or treatment switches if a high proportion ($\geq 33\%$) of patients in the control arm started new anti-cancer treatment or received subsequent PRRT treatment. In this case the main OS analysis would be conducted treating treatment as time-dependent variable and sensitivity analyses

would include Rank preserving structural failure time (RPSFT), Intent To Treat and censoring at time of switch.

Cox proportional hazard regression will also be used when adjusting for the co-variables

- primary tumour origin (GE-NET vs. P-NET),
- prior medical treatment (1st line vs. 2nd line),
- tumour grade (G1 vs. G2)
- baseline KPS (70, 80, 90 and 100),

The same covariates can be used for subgroup analyses as deemed appropriate and necessary. Other baseline characteristics such as but not limited to:

- Age (continuous or <65 vs. ≥65 or <75 vs. ≥75)
- Gender (M vs. F)
- Ethnic origin (White/Caucasian vs. others)
- ECOG (recalculated: 1=KPS 70 or 80 vs. 0=KPS 90 or 100)
- Time from primary diagnosis (continuous in months)
- Time from diagnosis of progression (continuous in months)
- Chromogranin A at baseline (continuous or >2*ULN vs. ≤2*ULN)
- Alkaline Phosphatase at baseline (continuous or >ULN vs. ≤ULN)
- BMI (continuous or ≤21 vs. 22 to 27 vs. >27)
- P-NET functioning status
- site of metastases (e.g. extra-hepatic vs. no extra-hepatic)
- Received SSA prior to baseline
- Received SSA prior to baseline and continue during treatment period

etc.

can also be used for subgroup analysis and/or Cox proportional Hazard regression with stepwise approach as deemed appropriate.

For time-to-event endpoint (PFS, OS), the proportional hazard assumption will be examined using appropriate method(s) including graphical diagnostics and/or statistical tests where needed.

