8.4 Clinical Laboratory Evaluations

Haematology: haemoglobin, haematocrit, mean corpuscular volume (MCV), mean corpuscular haemoglobin (MCH), white blood cell count (total and differential: leukocytes, neutrophils, eosinophils, basophils, lymphocytes, monocytes), red blood cells, platelets.

Biochemistry: sodium, potassium, chloride, calcium, glucose, creatinine, urea, albumin, total bilirubin, aspartate transaminase (AST), alanine transaminase (ALT), alkaline phosphatase (AP), gamma-glutamyl transferase (GGT), lipase, amylase, total protein,.

Clotting parameters: prothrombin time (quick), reagent-independent prothrombin ratio (international normalised ratio; INR), activated partial thromboplastin time (aPTT).

Urinalysis: specific gravity, pH, protein, glucose, blood, leukocytes, ketones, nitrite, albumin, creatinine; α -1-microglobulin will also be tested in urine but only in centres with adequate technical equipment and an established test method.

Tumour markers: Chromogranin-A, further markers

All lab parameters will be summarised by visit and treatment arms as continuous data (raw and change from baseline) or category data where appropriate (e.g. urine test with category units).

The following parameters will also be presented as boxplot graphs by visit and treatment arm: WBC, RBC, HB, Neutrophils, Lymphocytes, Platelets, alkaline phosphatase, bilirubin, AST, ALT, albumin, potassium, sodium, calcium, and tumour markers.

For the following parameters the percentage of patients experiencing CTCAE toxicity will also be summarised by worst CTCAE grades (all grades pooled and Grades 3 and 4 pooled) and by treatment arm for baseline and post first IMP dosing parts of the study:

ITM-LET-01	Statistical Analysis Plan
------------	---------------------------

Table 6: List of laboratory parameters to be analysed according to CTCAE guidelines

Lab parameter	CTCAE term:
Lymphocytes	Lymphocyte count increased
	Lymphocyte count decreased
Hb	Anaemia
Leukocytes	Leukocytosis
	White blood cell decreased
Platelets	Platelet count decreased
PNN	Neutrophil count decreased
Creatinine	Creatinine increased
Fasting blood glucose	Hypoglycaemia
	Hyperglycaemia
Calcium	Hypocalcaemia
	Hypercalcaemia
Potassium	Hypokalaemia
	Hyperkalaemia
Sodium	Hyponatremia
	Hypernatremia
GGT	GGT increased
Alkaline Phosphatase	Alkaline Phosphatase increased
AST	AST increased
ALT	ALT increased
Total bilirubin	Blood bilirubin increased
Albumin	Hypoalbuminemia

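### Tumour markers are assayed in each site's own laboratory, but the SAP's exploratory marker outputs pool them without a scale comparable across laboratories

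*Protocol*

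**What the plan says.** **Where the markers are measured.** Protocol 8.6.3 states that samples for CgA and other tumour markers "will be analysed in the institutional laboratories of each site according to local specifications". Protocol 8.3.5, which lists CgA among its tests, agrees: "Laboratory assessments will be performed by the institutional or local laboratories". Neither section names a common assay, unit or reference range. The number of laboratories may be large, since Protocol 4.3 states: "Potential patients for this study will be recruited by approximately 60 oncological centres in Europe, North America, South Africa and Australia". Under the COVID exception in Protocol 7.1, "blood samples may be collected and tested in the patient's local centre in a laboratory certified as per local requirements", so the laboratory can also change within a patient.

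**How the markers are analysed.**
- SAP 8.4 includes "Tumour markers: Chromogranin-A, further markers" in its laboratory list and then says: "All lab parameters will be summarised by visit and treatment arms as continuous data (raw and change from baseline" and so on. It adds: "The following parameters will also be presented as boxplot graphs by visit and treatment arm", and the list that follows ends with tumour markers.
- SAP 6 offers "Chromogranin A at baseline (continuous or >2*ULN vs. ≤2*ULN" among further baseline characteristics that may enter subgroup analyses or a stepwise Cox model. Use is left to judgement.
- SAP 3.4.3.1 and 7.3 plan to explore CgA and hormone levels against RECIST response, descriptively, by level subgroups and by correlations where relevant. No scale is given.
- Protocol 8.2.1.3 and SAP 3.4.3.1 describe optional biomarker response classes for patients with a raised baseline. These rest on the normal range and on percentage change from the patient's own earlier values.

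**The concern.** If two laboratories report the same serum on different scales, their values should not be averaged, plotted or correlated as one quantity. The SAP gives no ULN scaling and no laboratory adjustment for the outputs in 8.4, for the continuous form of the covariate in 6, or for the level-versus-response association in 3.4.3.1 and 7.3. SAP 5.8 only says that centre effects may be explored.

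Elsewhere the protocol centralises what it needs to compare: RECIST reading (8.7), pathology (8.1.4) and calculated GFR (8.3.9). Tumour markers get neither a central assay nor a common scale. What is at stake is the readability of the marker tables and plots, and the strength of any marker association, for a stated exploratory secondary objective (Protocol section 2, objective 5).

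**Working it through.** The plan gives no figure on this point to reproduce. The check has three parts.

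**1. Which outputs already sit on a comparable scale?**

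| Output | Place | Scale stated | Free of laboratory scale? |
|---|---|---|---|
| Marker tables and box plots by arm | SAP 8.4 | observed value; change from baseline | no |
| Baseline CgA, continuous | SAP 6 | none | no |
| Baseline CgA, cut at 2×ULN | SAP 6 | local ULN | largely |
| CgA level vs RECIST | SAP 3.4.3.1, 7.3 | none | not stated |
| Biomarker response classes (optional) | SAP 3.4.3.1, Protocol 8.2.1.3 | normal range; own baseline or nadir | largely |

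**2. Does change from baseline remove the problem?** Suppose a laboratory reports k times the true value x.
- Absolute change: k·x₁ − k·x₀ = k·(x₁ − x₀). The factor stays. A 40% fall from 3×ULN is −1.2 ULN units; a laboratory reading twice as high reports −2.4.
- Ratio: k·x₁ / k·x₀ = x₁/x₀. The factor cancels, but only within one laboratory. After a move from factor k₁ to k₂ the ratio is multiplied by k₂/k₁. With k₂/k₁ = 1.35, a stable patient shows a 35% rise, past the 25% used for biomarker progression.
- Multiple of ULN: k·x / (k·U) = x/U. The factor cancels if the laboratory's ULN moves with its scale.

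**3. How large could it be?** The documents give neither the between-patient nor the between-laboratory spread, so every input here is an assumption. Let s_P be the between-patient SD of log CgA and s_L the SD of the log laboratory factor. For a slope on log CgA, the fraction kept is s_P² / (s_P² + s_L²); in a Cox model this is an approximation.

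| s_L (fold difference at 1 SD) | s_P = 0.8 | s_P = 1.2 |
|---|---|---|
| 0.1 (1.11) | 0.64/0.65 = 0.98 | 1.44/1.45 = 0.99 |
| 0.3 (1.35) | 0.64/0.73 = 0.88 | 1.44/1.53 = 0.94 |
| 0.5 (1.65) | 0.64/0.89 = 0.72 | 1.44/1.69 = 0.85 |
| 0.7 (2.01) | 0.64/1.13 = 0.57 | 1.44/1.93 = 0.75 |

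A correlation shrinks by the square root of these factors, so at worst here by √0.57 = 0.75.

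A simulation of 300 patients in 60 laboratories (400 runs, median CgA 3×ULN, everyone falling 40%) covered the same range. The SD of absolute change was inflated 1.01 to 1.84 times. A common cut-off in unscaled units put 2.5% to 21% of patients on the wrong side. The second figure applies only if the level subgroups in SAP 7.3 are cut in unscaled units; it does not apply to the 2×ULN cut. After division by the local ULN the slope factor is 1.00, provided laboratories differ only by a factor that the ULN follows.

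**The case against.** The case for leaving the plan alone is substantial.

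- **Nothing confirmatory depends on it.** SAP 5.7 makes all tests other than PFS, ORR and OS exploratory. SAP 7.3 treats biomarkers descriptively, and the 8.4 outputs are descriptive safety tables. This stands and caps the severity.
- **The plan already has comparable measures.** A reader might infer that no marker analysis is on a common scale. The documents do not support that: the 2×ULN cut and the response classes are largely free of laboratory scale. However, the classes are given only as a possibility, and they do not govern the tables and plots in 8.4.
- **The continuous covariate is a permitted option.** A reader might infer that the SAP commits to an unscaled Cox covariate. It does not. The covariate is optional, listed beside the normalised form, and appears neither among the four named adjustment covariates in SAP 6 nor among the pre-specified subgroups in SAP 5.4.4.
- **Arm comparisons should not be biased.** A reader might infer that high-scale laboratories favour one arm. Randomisation is central and does not depend on laboratory, so scale balances in expectation. Site is not a stratification factor and centres average 300/60 = 5 patients, so chance imbalance is possible, but that is noise.
- **Medians, quartiles and rank tests are planned.** They blunt extreme laboratories, but ranking across unlike scales still mixes them.
- **Harmonisation may be specified elsewhere.** *Raw* in SAP 8.4 may simply mean observed value as opposed to change, and the data management plan and table mock-ups are not available here. Units may therefore be converted. That would not by itself remove a difference in assay calibration or reference range, if one exists.

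**Conclusion.** The point holds as a minor one. Locally assayed tumour markers are pooled by arm as observed values and changes in SAP 8.4, may enter a Cox model unscaled under SAP 6, and are related to RECIST response on an unstated scale in SAP 3.4.3.1 and 7.3. To the extent that local assays differ in scale, this adds noise and attenuates marker associations. The size is unknown: negligible if laboratories agree within about 10%, and a loss of a quarter to nearly half of a log-scale slope (factors 0.75 and 0.57) if they differ about two-fold. Those figures rest wholly on assumed spreads.

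PFS, ORR and OS, with their power and alpha, are untouched, and no systematic arm bias is expected. That last statement concerns randomised patients. Protocol 3.6.3 lets some patients at Sub-study C sites be allocated directly to PRRT, and the blacked-out text does not allow a judgement on how they enter the SAP 8.4 tables.

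**What to change.** Amend SAP 6, 7.3 and 8.4 as follows.

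- **8.4:** for tumour markers, make log(value/local ULN), and the percentage change or log-ratio to the patient's own baseline from the same laboratory, the main scales for tables and box plots. Values in original units may stay in listings.
- **7.3 (with 3.4.3.1):** use the same scales for the association between marker level and RECIST response.
- **6:** as baseline covariate, use the listed 2×ULN cut or log(value/local ULN) in place of the unscaled value. The ratio to own baseline cannot serve here, because at baseline it is 1 for everyone.
- **Data:** hold laboratory, unit and ULN with each marker result, and flag patients whose laboratory changed, including under the COVID exception.

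The cost is SAP wording and a little extra derivation, with no new samples. Local ULNs are already needed for the 2×ULN cut and for judging normalisation in the response classes. The limitation is that scaling helps only as far as each laboratory's ULN tracks its assay scale, and the SAP should say so.
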